## SYNOPSIS

Title	Asthma: Phenotyping Exacerbations 3
Acronym	APEX 3
Short title	Asthma: Phenotyping Exacerbations 3
Chief Investigator	[name]
Objectives	
Primary Objective
 

• To describe the symptom burden, lung function, inflammatory profile, and infection status in patients admitted to hospital with suspected asthma attacks.

 
Secondary Objectives
 

• Determine the proportion of patients hospitalised with suspected asthma attacks likely due to non-asthma pathology.

• Describe and assess the incidence of extra-pulmonary co-morbidities in patients hospitalised with asthma attacks.

• Assess incidence of risk factors for attacks based on patients' previous history.

• Assess patients' adherence with asthma medications.

• Compare the use of Forced Oscillation Technique (FOT) as a non-effort dependent measure of airway obstruction in suspected severe asthma attacks to a standard measure of airway obstruction Peak Expiratory Flow Rate (PEFR).

• Compare the use of Fractional Exhaled Nitric Oxide (FeNO) as a measure of airway inflammation against sputum and blood eosinophils.

• Describe objective and symptomatic treatment response and recovery from severe asthma attacks following hospital discharge.

Trial Configuration	A Single-Centre, Longitudinal, Observational Study
Setting	Secondary Care.
Sample size estimate	This is an observational, hypothesis-generating study, and due to the lack of previous data on this subject, a meaningful sample size calculation cannot be performed.
Number of participants	100

Eligibility criteria	
Inclusion Criteria:
 

• The ability to give fully informed consent

• Male or female aged <math>\geq 18</math> years of age.

• Admission with a suspected acute asthma attack.

• Able (in the investigator's opinion) and willing to comply with clinical investigation requirements.

 
Exclusion Criteria
 

• Other clinically significant respiratory diseases including predominant Chronic Obstructive Pulmonary Disease (COPD) and bronchiectasis.

• Any other clinically significant medical disease or uncontrolled concomitant disease that is likely, in the investigator's opinion, to impact the ability to participate in the study or the study results.

• Pregnant women, lactating women or women who are planning to become pregnant.

• Investigator determined apparent other cause for admission.

• Acute COVID infection.

• Non-English-speaking participants who are unable to comprehend the reasons for the study due to limitations in understanding the English language.

Description of interventions	

• The collection of medical history, demographic data, and concomitant medications.

• The incidence of upper airway symptoms will be assessed using the Sino-nasal Outcome Test (SNOT).

• The assessment of the incidence of Gastroesophageal Reflux Disease using the GERDQ questionnaire.

• The assessment of the incidence of vocal cord dysfunction using the Pittsburgh Vocal Cord Dysfunction (VCD) Index.

• The assessment of the incidence of dysfunctional breathing using the Nijmegen dysfunctional questionnaire.

• The assessment of the incidence of anxiety and depression using the Hospital Anxiety and Depression Scale (HADS).

• The assessment of the quality of life using the Acute Asthma Quality of Life Questionnaire.

• The assessment of medication adherence using the Medication Adherence Report Scale.

• The assessment of lung function by performing Fractional Exhaled Nitric Oxide (FeNO), Forced Oscillation Technique (FOT), Peak Expiratory Flow Rate (PEFR) and Spirometry.

• The collection of blood samples for laboratory analysis and storage for future research.

• The collection of sputum samples for sputum differential cell count, bacterial culture and sensitivity and storage for future research.

• The collection of nasal absorption samples for future cytokine profiling.

• The collection of samples via nasal lavage and throat swabs for viral identification.

• The collection of optional nasal brushing samples for RNA and DNA extraction.

Duration of study	Study duration: from January 2022 to July 2023.

Randomisation and blinding	Not Applicable
Outcome measures	

Assessment of cytokine levels in nasal lining fluid at attack and recovery visits.

The measurement of vitamin D levels in the blood on admission to the hospital.

Assessment of evidence of infection: Throat swab/nasal lavage for viral PCR, sputum for bacterial culture and sensitivity, CRP.

Assessment of incidence of extra-pulmonary co-morbidities: Questionnaires (SNOT, GERDQ, Pittsburgh VCD index, Nijmegen, HADS) and BMI.

A specific asthma history (polypharmacy, previous asthma attacks, triggers, Personalised Asthma Action Plan) for the assessment of risk factor for attack.

Assessment of adherence to medications (MARS, prescription records, inhaler technique) for the assessment of behavioural attack traits.

Assessment of airway obstruction at attack and recovery visits using peak expiratory flow rate (PEFR), spirometry, physician recorded expiratory wheeze and Forced Oscillation Technique (FOT).

Assessment of airway inflammation at attack and recovery visits using Fractional Exhaled Nitric Oxide (FeNO), sputum inflammatory cell count and blood eosinophil count.

Assessment of symptom burden at attack and recovery visits using the Acute AQLQ questionnaire.

Statistical methods	The main outcomes of the exacerbation are descriptive in nature, and no statistical tests are planned. We will, however, compare key findings at exacerbation visits with those undertaken at the follow-up visits, including: Paired tests (paired t-test or McNemar) will be used to examine changes in fractional exhaled nitric oxide (FeNO), parameters derived from Forced Oscillation Technique (FOT), the Acute Asthma Quality of Life Questionnaire (Acute AQLQ), sputum differential cell count, nasal absorption, haematology, and clinical chemistry values.

## ABBREVIATIONS

Acute AQLQ	Acute Asthma Quality of Life Questionnaire
AE	Adverse Event
CI	Chief Investigator overall
COPD	Chronic Obstructive Pulmonary Disease
CRF	Case Report Form
CRP	C-Reactive Protein
DMC	Data Monitoring Committee
FeNO	Fractional Exhaled Nitric Oxide
FEV1	Forced Expiratory Volume in 1 Second
FOT	Forced Oscillation Technique
GCP	Good Clinical Practice
GERDQ	Gastroesophageal Reflux Disease Questionnaire
HADS	Hospital Anxiety and Depression Scale
ICF	Informed Consent Form
MARS	Medicines Adherence Report Scale
MCS	Microscopy Culture Sensitivities
NHS	National Health Service
PI	Principal Investigator at a local centre
Pittsburgh (VCD) Index	Pittsburgh Vocal Cord Dysfunction (VCD) Index
PEFR	Peak Expiratory Flow Rate
PIS	Participant Information Sheet
PCR	polymerase chain reaction
REC	Research Ethics Committee
R&D	Research and Development department
SAE	Serious Adverse Event

Page 8 of 35

Phenotyping Asthma Exacerbations: A Longitudinal Cohort Study 3 (APEX 3)  
Protocol: Final Version 1.0 10.11.2021 IRAS: 304615

SNOT	Sino-nasal Outcome Test
T2	Type 2
WCC	White Cell Count

## STUDY BACKGROUND INFORMATION AND RATIONALE

Asthma is a common condition affecting 9.8 million people in the United Kingdom^1. Asthma attacks cause nearly 1500 deaths per year in the UK and account for over 90,000 hospital admissions and 1800 intensive care admissions costing at least 1 billion pounds a year.

Non-asthma conditions such as Vocal Cord Dysfunction and Dysfunctional Breathing Pattern can mimic severe asthma and lead to hospital admission and inappropriate asthma treatment with potentially harmful high dose corticosteroids. However, the proportion of patients admitted with these asthma mimics is unclear.

The use of biomarkers to guide treatment in stable asthma is now commonplace, but this prospect has not been fully explored in acute asthma attacks. Determining the type of inflammation underlying an attack can, however be tricky because many patients receive oral corticosteroid prior to, or soon after admission, which promptly and markedly affects the most accessible type 2 asthma (T2) biomarkers, the blood eosinophil count. Measurement of another T2 biomarker, fractional exhaled nitric oxide (FENO), during an attack may prove a useful measure of ongoing T2 airway inflammation, but this strategy requires assessment.

Airway obstruction in asthma attacks is assessed and confirmed by measuring peak expiratory flow and/or forced expiratory volumes. These measures are effort-dependent and can, therefore, be unreliable and misleading if improperly performed. We aim to evaluate the potential feasibility and utility of alternative diagnostic methods of assessing airway obstruction and measuring T2 biomarkers to see if these allow the distinction between actual asthma attacks and asthma attack mimics and also if they can distinguish different types of asthma attacks.

The pattern of recovery following asthma attacks is also not fully understood. Studies have reported varying recovery times and inconsistencies in the response of airway obstruction and T2 biomarkers to corticosteroid treatment in acute asthma.

We hypothesise that a significant proportion of patients admitted to hospital with suspected asthma attacks have an alternate cause for their clinical presentation. To further explore this, we propose an observational study to describe and investigate the characteristics of patients admitted with suspected severe asthma. We will assess the utility of point of care, non-invasive biomarker measurements in identifying pulmonary and extrapulmonary traits in patients hospitalised due to presumed asthma attack. A variety of study assessments will be performed at the baseline visit (exacerbation visit), and two follow up visits following hospital discharge. Results of study assessments obtained during each study visit will be compared and analysed. This is the first study to prospectively investigate acute asthma both during and following exacerbation episodes. This will allow a comprehensive understanding and description of pulmonary and extrapulmonary traits as well as the pattern of recovery following asthma attacks.

## STUDY OBJECTIVES AND PURPOSE

### PURPOSE

The purpose of this study is to describe the biological and physiological changes (pulmonary traits) and physical and psychological comorbidities (extrapulmonary traits) seen in patients requiring hospitalisation for presumed asthma attacks. The recovery and response to standard treatment for asthma attacks following discharge from the hospital will also be described.

The feasibility and utility of measuring non-invasive point of care biomarkers as a means of confirming and quantifying airway obstruction and detecting T2 airway inflammation will be assessed. Blood and sputum samples will be obtained for biomarker profiling.

This will enable the most comprehensive description of asthma attack phenotypes requiring hospitalisation and recovery from these events to date.

### PRIMARY OBJECTIVE

- To describe the symptom burden, lung function, inflammatory profile, and infection status in patients admitted to hospital with suspected asthma attacks.

### SECONDARY OBJECTIVES

- Determine the proportion of patients hospitalised with suspected asthma attacks likely due to non-asthma pathology.
- Describe and assess the incidence of extra-pulmonary co-morbidities in patients hospitalised with asthma attacks.
- Assess incidence of risk factors for attacks based on patients' previous history.
- Assess patients' adherence with asthma medications.
- Compare the use of Forced Oscillation Technique (FOT) as a non-effort dependent measure of airway obstruction in suspected severe asthma attacks to a standard measure of airway obstruction Peak Expiratory Flow Rate (PEFR).
- Compare the use of Fractional Exhaled Nitric Oxide (FeNO) as a measure of airway inflammation against sputum and blood eosinophils.
- Describe objective and symptomatic treatment response and recovery from severe asthma attacks following hospital discharge.

## DETAILS OF PRODUCT(S)

### Description of Products

#### Saline

Sterile saline solution of varying concentrations will be used in the sputum induction and nasal lavage procedures. This will be prepared from a commercially available 7% solution.

#### Salbutamol

An inhaled short-acting beta2agonist, Salbutamol, will be administered. This will be given prior to the sputum induction. All participants will have salbutamol prescribed to them as part of their routine care.

#### Packaging and labelling

All products described above are those used in standard NHS practice.

#### Storage, dispensing and return

All products described above are routinely stored in the Nottingham Respiratory Research Unit (NRRU) Clinical Trials Unit (CTU) at the City Hospital campus.

#### Placebo

No Placebo is being used.

#### Known Side Effects

Sputum induction in patients with asthma can cause a small fall in lung function (FEV1). This risk will be minimised with pre-treatment with Salbutamol.

Known side effects of beta2agonists, such as Salbutamol, include fine tremor, headaches, palpitations and tachycardia.

## STUDY DESIGN

### STUDY CONFIGURATION

This is a single centre observational, longitudinal study. The study will aim to recruit 100 patients hospitalised due to a suspected asthma attack. They will be identified from the Respiratory admission units or inpatient wards at the Nottingham City Hospital or the emergency department at Queens Medical Centre.

The initial assessment will take place at the earliest timepoint possible following hospital admission with a suspected asthma attack. A range of investigations, including lung function tests, blood tests, and questionnaires, will be performed. A follow-up visit will be arranged, which will take place approximately two weeks after hospital discharge at the Nottingham Respiratory Research Unit, at which further lung function tests, blood tests and questionnaires will be performed.

A subsequent telephone follow-up visit will be scheduled at around four weeks after hospital discharge, at which additional questionnaires will be performed to determine the degree of symptomatic recovery. A PhD student will perform the majority of study recruitment and study interventions under the fellow's direct supervision.

### Primary endpoint

As this is an observational study with a primary objective that is descriptive in nature, there are no endpoints, and all outcome measures are equally essential in describing the primary objective; outcome measures include:

- Assessment of cytokine levels in nasal lining fluid at attack and recovery visits.
- The measurement of vitamin D levels in the blood on admission to the hospital.
- Assessment of evidence of infection: Throat swab/nasal lavage for viral PCR, sputum for bacterial culture and sensitivity, CRP.
- Assessment of incidence of extra-pulmonary co-morbidities: Questionnaires (SNOT, GERDQ, Pittsburgh VCD index, Nijmegen, HADS) and BMI.
- A specific asthma history (polypharmacy, previous asthma attacks, triggers, Personalised Asthma Action Plan) for the assessment of risk factor for attack.
- Assessment of adherence to medications (MARS, prescription records, inhaler technique) for the assessment of behavioural attack traits.
- Assessment of airway obstruction at attack and recovery visits using peak expiratory flow rate (PEFR), spirometry, physician recorded expiratory wheeze and Forced Oscillation Technique (FOT).
- Assessment of airway inflammation at attack and recovery visits using Fractional Exhaled Nitric Oxide (FeNO), sputum inflammatory cell count and blood eosinophil count.
- Assessment of symptom burden at attack and recovery visits using the Acute AQLQ questionnaire.

## **Safety endpoints**

As this is an observational study, there are no defined safety endpoints, although investigations at the time of exacerbation will not be performed if there are safety concerns.

## **Stopping rules and discontinuation**

As this is an observational study, there are no planned stopping criteria other than for individual participants who wish to stop, or who cannot be contacted.

## **RANDOMIZATION AND BLINDING**

There is no randomisation in this cohort study.

## **STUDY MANAGEMENT**

The study will be managed by a Clinical Management Group, who will meet at least monthly to monitor the progress of the study. This will consist of the Chief Investigator, the Co-Investigator (s), the Asthma Research Development Manager, the Database Manager and the Research Nursing Team.

The Chief Investigator has overall responsibility for the study and shall oversee all study management. The data custodian will be the Chief Investigator.

## **DURATION OF THE STUDY AND PARTICIPANT INVOLVEMENT**

### **Study Duration:**

We plan to recruit approximately 100 patients over a period of 18 months. The total duration of the study will be approximately 2.5 years. The study will begin in January 2022 and finish in July 2023.

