### **Participant Duration:**

The baseline (Attack) visit will take place at the earliest timepoint possible following hospital admission. A follow up visit will be arranged, approximately 2 weeks after hospital discharge. A third telephone follow up visit will be arranged approximately 4 weeks after hospital discharge.

Study participants will be participating in the study from the time of consent (earliest timepoint possible following hospital admission) up to approximately four weeks following hospital discharge. This could be from 4-12 weeks depending on the length of hospital stay. The maximum length of participation in the study is 12 weeks per participant.

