## **End of the Trial**

The end of the study will be the last visit of the last participant.

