### **Expected duration of participant participation**

Study participants will be participating in the study for 4-12 weeks depending on the length of hospital stay. The maximum length of participation in the study is 12 weeks per participant.

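### Does a stated total duration of 2.5 years, set beside dates that span about 18 months, call for a change to the plan?

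*Combined protocol and SAP*

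**What the plan says.** The Study Duration section makes three statements about time. On recruitment: "We plan to recruit approximately 100 patients over a period of 18 months". On the whole study: "The total duration of the study will be approximately 2.5 years. The study will begin in January 2022 and finish in July 2023". The Synopsis repeats only the dates: "Study duration: from January 2022 to July 2023".

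Two other sections bear on the timeline. Participant Duration describes participation as running from consent to about four weeks after discharge: "This could be from 4-12 weeks depending on the length of hospital stay". The section on expected duration of participation adds a ceiling: "The maximum length of participation in the study is 12 weeks per participant". End of the Trial sets the closing point: "The end of the study will be the last visit of the last participant".

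The assessment schedule has a second visit at day 14 and a telephone visit at day 28, each with a margin of two days. Study Configuration counts these from hospital discharge. No section describes a separate period for analysis or write-up.

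**The concern.** The sentence giving 2.5 years is followed directly by dates that allow little more than a year and a half. A word such as approximately cannot cover a difference of about a year. A reader who wants to know when the study ends gets July 2023 from one sentence and about July 2024 from the other.

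There is a second tension within the dates themselves. If recruitment takes 18 months from January 2022, it closes at about the point where the study is said to finish, yet the last participants still need at least four weeks of follow-up and possibly 12. If the July 2023 date were enforced as a hard stop, late entrants could lose their day 28 telephone call or their second visit. Because the analysis is of complete cases, they would then drop out of the paired comparisons. The other possibility is that recruitment would have to close early and fall short of about 100.

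**Working it through.** **Inputs.** Start January 2022, finish July 2023, total 2.5 years and recruitment of about 100 over 18 months (Study Duration). Participation of 4 to 12 weeks (Participant Duration). One month is taken as 365.25/12 = 30.44 days. The documents give months only, so the days are assumptions and the range is shown.

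**1. The plan's own total.** 2.5 × 12 = 30 months. From 1 January 2022 this runs to 1 July 2024.

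**2. Span of the stated dates.**

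| Reading | Days | Months | 30 minus span |
|---|---|---|---|
| 1 Jan 2022 to 31 Jul 2023 (widest) | 576 | 18.9 | 11.1 |
| 15 Jan 2022 to 15 Jul 2023 (same day of month) | 546 | 17.9 | 12.1 |
| 31 Jan 2022 to 1 Jul 2023 (narrowest) | 516 | 16.9 | 13.1 |

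No reading reproduces 30 months.

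**3. Recruitment plus participation.**

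- At 4 weeks: 18 + 28/30.44 = 18.9 months.
- At 12 weeks: 18 + 84/30.44 = 20.8 months.

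On the widest reading, the time left after recruitment is (576 − 18 × 30.44)/7 = 4.0 weeks, so only the minimum participation fits. On the same-day reading, recruitment uses the whole span.

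**4. When the last visit would fall.** Assume recruitment from 1 January 2022 to 30 June 2023. A participant entering on the last day finishes on 28 July 2023 at 4 weeks, 25 August at 8 weeks and 22 September at 12 weeks. Participation ends about four weeks after discharge, so 12 weeks implies a stay of about 12 − 4 = 8 weeks after consent. The documents give no length-of-stay figures.

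**5. Who could be affected.** With a finish on 31 July 2023 (an assumption), 31 July − 84 days = 8 May, so only entrants after 8 May could overrun. An entrant on 1 June has 60 days, or 8.6 weeks, which allows a stay of about 8.6 − 4 = 4.6 weeks. With a finish on 1 July 2023 the cut-off moves to 8 April. Entrants in the final four weeks could then not finish even a minimum follow-up by that date. At 100/18 = 5.6 a month, that is 5.6 × 28/30.44 = about 5 people.

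**6. If recruitment were shortened.** Reserving 12 weeks inside the widest span leaves (576 − 84)/30.44 = 16.2 months, or 16.2 × 5.6 = about 90 participants at the planned rate. For a proportion of 50% (an illustrative value), the 95% half-width is 1.96 × √(0.25/100) = 9.8 percentage points with 100 and 1.96 × √(0.25/90) = 10.3 with 90.

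**7. What depends on the total duration.**

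- The sample size section gives no calculation.
- Visits are tied to discharge.
- The Statistics section compares attack and follow-up visits within participants.
- The protocol sets no stopping criteria for the study as a whole and no interim analysis.
- The study ends with the last participant's last visit.

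None of these takes the 2.5-year figure as an input.

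**The case for a change.** The strongest argument for a correction is that the contradiction is plain and the innocent explanations are not in the text. Analysis time could account for an extra year, but no section says so, and the Study Duration section has the study finishing in July 2023. Set-up time after the protocol was finalised does not account for it either. The footer reads "Protocol: Final Version 1.0 10.11.2021", and from that date to 31 July 2023 is 628 days, or 20.6 months, though this says nothing about earlier set-up. The choice between the figures also has a practical side. With 30 months the recruitment and follow-up fit easily, and with the dates they barely fit. The sponsor may stop the study for poor enrolment, and an ethics committee is entitled to one clear timeline.

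The contradiction and the tight fit stand. What does not stand is that readers are left unable to plan. January 2022 plus 18 months is about July 2023, so the recruitment period and both statements of the dates agree broadly, and 2.5 years stands alone. That makes it the likely slip, although the documents do not prove which figure is wrong. The overrun to late September is a worst case that needs a very long admission in one of the last people recruited. The provision on discontinuation by the sponsor names enrolment goals but attaches no date or total duration to them.

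**Conclusion.** The inconsistency is real, at 11.1 to 13.1 months, but it is clerical and no change to the plan follows. The statement "The total duration of the study will be approximately 2.5 years" drives no sample size, test, threshold, visit or safety rule. A study team following the protocol would recruit for about 18 months and see each participant through to the call four weeks after discharge. It would then close with the last of those calls, because the end of the study is defined by that event. If the last entrants ran past July 2023, the date would slip by weeks, at most about 53 days on a 1 January start (31 July to 22 September), and their data would still be complete. The protocol already lets logistical or administrative amendments take effect at once, with the ethics committee informed.

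The conclusion rests on two assumptions: that the end-of-study definition governs over the calendar date, and that the target is approximate, as stated. If the calendar date were enforced instead and recruitment closed early enough to reserve the full 12 weeks, about 90 would be recruited at the planned rate. For this descriptive study that widens a confidence interval by about half a percentage point on each side. A single consistent timeline would read better, but it would not alter any result.
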